10.5.1.3 Subgroup Analyses of Co-primary Efficacy Endpoints

Subgroup analyses on the co-primary efficacy endpoints will be conducted using the subgroups specified in Section 7.4. Treatment effect differences among subgroups, which represent subgroup by treatment interactions, will be estimated based on statistics from the subgroup repeated measures models.

For subgroup analyses, the stratification factors and baseline covariates from the eCRF will be used. Differences in stratum assignment between data collection via IVRS/IWRS and eCRF will be tabulated.

10.5.2 Analyses of Co-secondary Efficacy Endpoints

The statistical model and testing of the tier 1 co-secondary efficacy endpoints will be similar to the primary analysis of the co-primary endpoints. The co-secondary efficacy endpoints of LDL-C target achievement as defined in Section 6.3 will be analyzed using the Cochran-Mantel-Haenszel (CMH) test adjusted by the stratification factors.

Analyses of the tier 2 co-secondary efficacy endpoints will use the same analysis model as the tier 1 endpoints, and testing will use a union-intersection test. For each tier 2 endpoint, the alternative hypothesis of the union-intersection test is that at least 1 of the treatment effects from the co-endpoints is not equal to zero.

Multiplicity adjustment procedure of testing evolocumab in combination with atorvastatin vs. placebo in combination with atorvastatin for co-secondary endpoints is defined in Section 10.1.

10.5.3 Analyses of Tertiary Efficacy Endpoints

Analysis of the co-tertiary efficacy endpoints will be similar to the primary analysis of the primary endpoints. No multiplicity adjustment will be applied.

10.5.4 Analyses of Exploratory Endpoints

Exploratory endpoints related to lipid parameters and PCSK9 will be summarized by randomized treatment group and by scheduled visit using descriptive statistics.

Non-coronary revascularizations will be collected on the eCRF and will not be adjudicated. Subject incidence of non-coronary revascularizations will be summarized.

A shift table for hsCRP will be provided, for levels at baseline to maximum post-baseline value (<1, 1-3, >3 mg/L), by treatment group.

HbA1c will be summarized at each scheduled assessment by treatment group.

Fasting and postprandial laboratory parameters of interest (including MMTT Extended Timepoints Substudy assessments) will be summarized at each scheduled assessment by treatment group.

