7.7.7 Mixed Meal Tolerance Test Extended Timepoints Substudy

6

33

54

Where offered and locally approved for the study center, subjects can be invited to participate in a MMTT Extended Timepoints Substudy. Enrollment into the substudy will be capped at approximately 240 subjects. The substudy consists of 2 additional postprandial blood draws in the MMTT on day 1 and week 12 as per Section 7.7.6. Postprandial blood draws for subjects participating in the substudy will be at the following timepoints after consumption of the standardized meal:

• 60 ± 10 min

Total Fat

Totals

Carbohydrate

- 120 ± 10 min
- 180 ± 10 min

20

55

100

The same postprandial analytes as per Section 7.7.6 will be measured at each of these timepoints.

8. WITHDRAWAL FROM TREATMENT, PROCEDURES, AND STUDY 8.1 Subject's Decision to Withdraw

Subjects have the right to withdraw from the study at any time and for any reason without prejudice to their future medical care by the physician or at the institution.

Subjects (or a legally acceptable representative) can decline to continue receiving IP and/or other protocol-required therapies or procedures at any time during the study but continue participation in the study. If this occurs, the Investigator is to discuss with the subject the appropriate processes for discontinuation from IP or other protocol-required therapies and must discuss with the subject the options for continuation of the Schedule of Assessments (Table 1) and collection of data, including endpoints and adverse events. The Investigator must document the change to the Schedule of Assessments (Table 1) and the level of follow-up that is agreed to by the subject (eg, in person, by telephone/mail, through family/friends, in correspondence/communication with other physicians, from review of the medical records).

Withdrawal of consent for a study means that the subject does not wish to receive further protocol-required therapies or procedures, and the subject does not wish to or is unable to continue further study participation. Subject data up to withdrawal of consent will be included in the analysis of the study, and where permitted, publically available data can be included after withdrawal of consent. The Investigator is to discuss with the subject appropriate procedures for withdrawal from the study. The investigator should ask the subject's consent to perform the procedures listed under the final study visit.

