2.4 Exploratory

- To describe the effects over time of SC evolocumab Q2W and QM in combination with atorvastatin QD, compared with placebo Q2W and QM, in combination with atorvastatin QD, on change from baseline in proprotein convertase subtilisin/kexin type 9 (PCSK9) levels and on change from baseline and percent change from baseline of LDL-C, total cholesterol, non-HDL-C, ApoB100, total cholesterol/HDL-C ratio, ApoB100/ApoA1 ratio, triglycerides, VLDL-C, HDL-C, ApoA1, and Lp(a), and categorical change from baseline in high sensitivity C-reactive protein (hsCRP) in diabetic subjects with hyperlipidemia or mixed dyslipidemia
- To explore the effect of SC evolocumab Q2W and QM in combination with atorvastatin QD, compared with placebo Q2W and QM, in combination with atorvastatin QD, on fasting and postprandial plasma laboratory parameters of interest
- To investigate the relationship between novel and established biochemical cardiovascular and lipid biomarkers and effects of evolocumab
- To investigate potential correlations of study data including the subject response to evolocumab with genetic variation in markers of PCSK9 signaling, low-density lipoprotein receptor (LDLR) turnover, cholesterol metabolism, inflammation, and plaque stability in subjects consenting to the optional pharmacogenetics analysis
- To explore evolocumab population pharmacokinetics in diabetic subjects
- To explore evolocumab exposure/response relationships in diabetic subjects

3. Study Overview

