The study includes collection of biomarker samples and, where approved by the institutional review board and/or independent ethics committee (IRB/IEC) and applicable regulatory and other authorities, subjects will be invited to consent to pharmacogenetics analyses. All subjects will complete a mixed meal tolerance test (MMTT) at the day 1 and week 12 study visits with a fasting blood collection (0 hours) and 1 postprandial blood collection 2 hours (± 10 min) after the meal and up to approximately 240 subjects will participate in a MMTT Extended Timepoints Substudy with 2 additional postprandial blood draws at 1 hour (± 10 min) and 3 hours (± 10 min) after the meal. End of study (EOS) for subjects on QM IP is at the week 12 visit. EOS for subjects on Q2W IP is by contact (e.g., phone call) from the site at week 14 for any potential adverse events (AEs), adverse device effects (ADEs), and serious AEs (SAEs). Subjects will be encouraged to complete all planned visits regardless of their adherence to IP administration. Accumulating safety and other data will be reviewed by an independent external Data Monitoring Committee (DMC). Where analyte concentrations are provided in mmol/L, it is for investigator convenience.

Conventional concentrations (mg/mL) will be used for the protocol, including for eligibility determination.

The overall study design is described by a study schema at the end of the protocol synopsis section. Detailed study procedures are provided in Protocol Section 7.

The study endpoints are defined in Section 4.1

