10.6.8 Exposure to Concomitant Medication

The number and proportion of subjects receiving the lipid regulating medications of interest (MOI) will be summarized by category and preferred term for each treatment group as coded by the World Health Organization Drug (WHO Drug) dictionary.

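### SAP 10.5.4 plans only by-arm summaries for the meal-test parameters and HbA1c; a baseline-adjusted placebo difference with a 95% CI, and a rule for four-point profiles, would be a cheap improvement

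*SAP*

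**What the plan says.** The objective in SAP 2.4 is comparative: "To explore the effect of SC evolocumab Q2W and QM in combination with atorvastatin QD, compared with placebo Q2W and QM", with the outcome given as the effect "on fasting and postprandial plasma laboratory parameters of interest". It is one of several exploratory objectives.

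The data behind it are of two kinds. SAP 3.1 says "All subjects will complete a mixed meal tolerance test (MMTT) at the day 1 and week 12 study visits", which gives 0 and 120 min samples in everyone. The 60 and 180 min samples come from a substudy capped at about 240 subjects. Protocol 7.7.7 describes entry to it as follows: "Where offered and locally approved for the study center, subjects can be invited to participate".

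The analysis in SAP 10.5.4 is: "Fasting and postprandial laboratory parameters of interest (including MMTT Extended Timepoints Substudy assessments) will be summarized at each scheduled assessment by treatment group". For HbA1c it is: "HbA1c will be summarized at each scheduled assessment by treatment group". SAP 10.1 defines a continuous summary as the number of subjects, mean, median, SD or SE, minimum and maximum. Neither document specifies, for these parameters, a difference from placebo, a confidence interval, a baseline adjustment, a meal increment or an AUC. Nor does either say which subjects would enter a profile over the four meal times.

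**The concern.** The objective asks for an effect compared with placebo, but the planned output stops at separate columns per arm. Two quantities of natural interest from a repeated meal test are within-subject: the rise from fasting to 120 min, and the change from Day 1 to week 12. A table that treats each timepoint separately discards the pairing, although every subject is tested at both visits.

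The meal times also rest on different sets of subjects. If someone later draws a 0-60-120-180 min curve or computes an AUC from the four tabulated means, alternate points would come from different populations.

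At stake is the precision and pre-specification of an exploratory estimate drawn from about 900 subjects who each take two meal tests. If the contrast is not written down before unblinding, the choice of analyte, timepoint and adjustment is made afterwards.

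**Working it through.** **Inputs from the documents.** 300 evolocumab and 150 placebo subjects per dose frequency, with 2% randomized but not dosed (SAP 3.2); allocation 2:2:1:1 (SAP 3.1); substudy cap of about 240 (Protocol 7.7.7).

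**Assumptions.** The documents give no correlations. The Day 1 to week 12 correlation rho is taken as 0.3 to 0.7. The 0 to 120 min correlation r within a visit is taken as 0.5 and 0.8. Differences are in SD units, with a common SD.

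**Group sizes.** 300 × 0.98 = 294 and 150 × 0.98 = 147. In the substudy, 240 × 2/6 = 80 and 240 × 1/6 = 40 are expected per frequency.

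**The plan's own figure.** The plan gives no precision or power for the MMTT. Its LDL-C power can be reproduced with the same counts. For a difference of 30 and SD 30, the standardized effect is 1/sqrt(1/294 + 1/147) = 1/0.1010 = 9.90, and 9.90 − 1.96 = 7.94. Power therefore exceeds 99.9%, consistent with the stated figure of at least 99%.

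**What the planned tables already allow.** The unadjusted 95% CI half-width at one timepoint is 1.96 × sqrt(1/n1 + 1/n2):

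- 0 and 120 min: 1.96 × 0.1010 = 0.198 SD
- 60 and 180 min: 1.96 × sqrt(1/80 + 1/40) = 1.96 × 0.1936 = 0.380 SD
- ratio of standard errors: 0.1936/0.1010 = 1.92

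**What baseline adjustment adds.** ANCOVA multiplies the variance by 1 − rho² and the half-width by sqrt(1 − rho²). For 294 vs 147:

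| Assumed rho | Variance reduction | Half-width (SD) | Narrowing |
|---|---|---|---|
| none | – | 0.198 | – |
| 0.3 | 9% | 0.189 | 5% |
| 0.5 | 25% | 0.171 | 13% |
| 0.7 | 49% | 0.141 | 29% |

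This cannot be recovered from by-visit summaries, because they do not report rho.

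**The meal increment.** Within an arm, Var(120 − 0) = s0² + s120² − 2·r·s0·s120, which is 2s²(1 − r) when the SDs are equal. The tables give s0 and s120 but not r. Treating the two times as independent gives 2s², which overstates the SE by 1/sqrt(1 − r): 1.41-fold at r = 0.5 and 2.24-fold at r = 0.8. A reader can subtract the means but cannot attach a valid interval.

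**The case against.** The strongest reply is that the analysis is exploratory and proportionate. SAP 10.5.4 treats the exploratory lipid and PCSK9 endpoints descriptively as well, and keeps models for the primary, secondary and tertiary endpoints. The randomized placebo arms stand alongside, and n, mean and SD yield an unadjusted contrast with its interval. SAP 10.6.2 adds change from baseline for select laboratory parameters, with reference to the analyte list in the protocol, so some meal-test analytes may be covered. Fasting LDL-C, triglycerides, HDL-C and VLDL-C already have modelled contrasts. The SAP plans no four-point curve, and different denominators do not bias the arm comparison at a single timepoint as long as substudy entry does not depend on arm. Nothing in the documents suggests that it does.

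All of this stands, and it rules out two stronger readings. A reader might infer that the objective cannot be answered. That is not so, since an unadjusted randomized comparison is available at each timepoint. A reader might also infer that the plan will produce an artefactual curve. That would need a joined profile, which the SAP does not call for.

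The reply does not supply the adjusted contrast or the increment with its uncertainty. SAP 10.6.2 leaves its parameters unnamed and specifies neither intervals nor meal times.

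**Conclusion.** The point holds as a low-priority improvement. SAP 10.5.4 answers a question worded as a comparison with summaries only. The missing pieces are a pre-specified baseline-adjusted difference from placebo, the increment with its interval, and a rule on who enters a four-point profile or AUC. The gain is a variance reduction of 9% at rho 0.3 to 49% at rho 0.7, and rho is an assumption. The 80 vs 40 split is an expectation under the cap and the allocation ratio.

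Two limits apply. The comparative objective covers the fasting and postprandial parameters. HbA1c is only listed as an exploratory endpoint, so treating it alike is a matter of consistency. And this is one exploratory objective in a trial whose primary objective is LDL-C, so no confirmatory conclusion is affected.

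A reader might further infer that HbA1c is uninterpretable because SAP 10.6.8 tabulates only lipid drugs ("The number and proportion of subjects receiving the lipid regulating medications of interest (MOI) will be summarized"). The documents do not support that. Inclusion criterion 103 requires stable diabetes therapy that is not expected to change. Protocol 9.2.1 makes laboratory changes that require a therapy adjustment adverse events, and these are tabulated. No figure in the documents shows that changes in therapy would mask an HbA1c effect.

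**What to change.** In SAP 10.5.4, within each dose frequency:

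1. For each MMTT analyte, report the week 12 evolocumab-minus-placebo difference with 95% CI for the fasting value and for the per-subject 120-minus-0 min increment. Use ANCOVA on the Day 1 value of the same quantity and the stratification factors. Fasting lipids already modelled elsewhere in the SAP need not be repeated.
2. Do the same for HbA1c, adjusting for the screening value, because Protocol Table 1 schedules no Day 1 sample.
3. Restrict any four-point profile or AUC 0-180 min to substudy subjects with all four samples at that visit.
4. Define Day 1 and week 12 values by meal time. The generic baseline rule (SAP 6.2) and the rule for several records on one day (SAP Appendix A) state no exception for the MMTT.
5. Label the results descriptive, without p-values.

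The cost is SAP wording and a few extra tables from data already collected. The drawback is more exploratory intervals without multiplicity control. The alpha plan is unchanged.

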(Giugliano et al, 2012; Koren et al, 2012; Sullivan et al, 2012; Raal et al, 2012). Treatment with evolocumab as monotherapy or in combination with statins (or other lipid lowering therapies) was effective in lowering serum concentrations of LDL-C, total cholesterol, ApoB100, VLDL-C, triglycerides, Lp(a), non-HDL-C, total cholesterol/HDL-C ratio, ApoB100/ApoA1 ratio, and PCSK9, and in increasing serum concentrations of HDL-C and ApoA1, in subjects with hyperlipidemia or mixed dyslipidemia (including heterozygous familial hypercholesterolemia and statin-intolerant subjects). Of the 6 evolocumab doses tested in phase 2, SC doses of 140 mg Q2W and 420 mg Q4W resulted in the greatest effects on lipid parameters and produced comparable results over the dosing interval.

Sensitivity analyses and non-parametric analyses confirmed that the primary endpoint analysis of efficacy was robust. Subgroup analyses of the primary efficacy endpoint of percent change in LDL-C from baseline to week 12 demonstrated consistent treatment effects across all subgroups including sex, presence or absence of diabetes, presence or absence of metabolic syndrome, screening LDL-C < or \geq 130 mg/dL, baseline triglyceride level, age (< 65 or \geq 65 years), intensive statin use at baseline (yes/no), and race.

For further details on evolocumab efficacy results refer to the AMG 145 Investigator's Brochure.

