3. EXPERIMENTAL PLAN

3.1 Study Design

This is a phase 3, multicenter, double-blind, randomized, stratified, placebo-controlled study of evolocumab for diabetic subjects with hyperlipidemia or mixed dyslipidemia. After undergoing screening procedures, including laboratory assessments and a screening placebo injection, approximately 900 subjects meeting eligibility criteria and completing at least 4 weeks of lipid stabilization on atorvastatin 20 mg QD will be randomized 2:2:1:1 into the following treatment arms:

- evolocumab SC 140 mg Q2W and atorvastatin PO 20 mg QD
- evolocumab SC 420 mg QM and atorvastatin PO 20 mg QD
- placebo SC Q2W and atorvastatin PO 20 mg QD, or
- placebo SC QM and atorvastatin PO 20 mg QD.

The sample size for each of the evolocumab plus atorvastatin dosing regimens will be approximately 300 subjects. The sample size for each of the placebo plus atorvastatin dosing regimens will be approximately 150 subjects.

Randomization into the 4 treatment groups will be stratified by entry statin therapy (no statin use vs non-intensive statin use vs intensive statin use [see Appendix D]) and by the site's geographic region. Treatment and follow-up period will be 12 weeks with an additional phone call or other subject contact at week 14 for subjects receiving IP Q2W.

Evolocumab and placebo SC will be administered at the study site or appropriate non-investigator site settings, eg, at the subject's home, per protocol Section 6 and Section 7 by spring-based prefilled autoinjector/pen (prefilled Al/Pen) for subjects receiving IP Q2W and by 3.5 mL Personal Injector for subjects receiving IP QM. The dose frequencies of Q2W and QM will not be blinded but the identity of IP (evolocumab or matching SC placebo) will be blinded. Post-IP treatment central laboratory results of the lipid panel, ApoA1, ApoB100, ApoB48, free fatty acids, chylomicrons, lipoprotein(a), PCSK9, insulin, proinsulin, C-peptide, glucagon, IL-6, adiponectin, vitamin E, PK, and high sensitivity C-reactive protein (hsCRP) will be blinded until unblinding of the clinical database and will not be reported to the investigator post-screening. Investigators should not perform non-protocol testing of these analytes during a subject's study participation and until at least 12 weeks after last IP administration, or the subject's end of study, whichever is later.

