7.7.6 Mixed Meal Tolerance Test (All Subjects)

A liquid mixed meal tolerance test (MMTT) will be performed after an overnight fast (no food or drinks other than water for \geq 9 hours) at the day 1 and the week 12 study visit. Each MMTT should be done at approximately the same time of day throughout the study (\pm 2 hours). The fasting venous blood samples at each of these 2 visits should be collected as close as possible before consuming a standardized mixed meal (see below) and before the subject receives any food or drink (other than water) or investigational product. Subjects are then fed a standardized mixed meal, as defined in Table 3 below, for example Boost[®]. The same type standardized mixed meal should be used for day 1 and for week 12.

The beginning of the consumption of the liquid mixed meal is considered time "0" of the MMTT. Postprandial blood samples are collected at 120 ± 10 min after consumption of the standardized mixed meal for assessment of the following analytes:

Table 3. Standardized Mixed MealContent componentGramsGrams %Calories (kcal)Calories %Protein15286025

11

61

100

48

132

240

 plasma glucose, insulin, proinsulin, C-peptide, free fatty acids, glucagon, lipids, chylomicrons, ApoB48, IL-6, adiponectin, vitamin E.

^aComponent weight in standardized mixed meal used can differ but total calories should not differ by more than \pm 10% of 240 kcal. The same type standard mixed meal should be used for day 1 and week 12.

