3.1 Study Design

This is a phase 3, multicenter, double-blind, randomized, stratified, placebo-controlled study of evolocumab for diabetic subjects with hyperlipidemia or mixed dyslipidemia. After undergoing screening procedures, including laboratory assessments and a screening placebo injection, approximately 900 subjects meeting eligibility criteria and completing at least 4 weeks of lipid stabilization on atorvastatin 20 mg QD will be randomized 2:2:1:1 into the following treatment arms:

- evolocumab SC 140 mg Q2W and atorvastatin PO 20 mg QD
- evolocumab SC 420 mg QM and atorvastatin PO 20 mg QD
- placebo SC Q2W and atorvastatin PO 20 mg QD, or
- placebo SC QM and atorvastatin PO 20 mg QD.

The sample size for each of the evolocumab plus atorvastatin dosing regimens will be approximately 300 subjects. The sample size for each of the placebo plus atorvastatin dosing regimens will be approximately 150 subjects.

Randomization into the 4 treatment groups will be stratified by entry statin therapy (no statin use vs non-intensive statin use vs intensive statin use [see Appendix C]) and by

the site's geographic region (China, Korea, other countries). Treatment and follow-up period will be 12 weeks with an additional phone call or other subject contact at week 14 for subjects receiving investigational product (IP) Q2W.

Evolocumab and placebo SC will be administered at the study site or appropriate noninvestigator site settings, e.g., at the subject's home, per protocol Section 6 and Section 7 by spring-based prefilled autoinjector/pen (prefilled Al/Pen) for subjects receiving IP Q2W and by 3.5 mL Personal Injector for subjects receiving IP QM. The dose frequencies of Q2W and QM will not be blinded but the identity of IP (evolocumab or matching SC placebo) will be blinded. Post-IP treatment central laboratory results of the lipid panel, ApoA1, ApoB100, ApoB48, free fatty acids, chylomicrons, lipoprotein(a), PCSK9, insulin, proinsulin, C-peptide, glucagon, IL-6, adiponectin, vitamin E, PK, and high sensitivity C-reactive protein (hsCRP) will be blinded until unblinding of the clinical database and will not be reported to the investigator post-screening. Investigators should not perform non-protocol testing of these analytes during a subject's study participation and until at least 12 weeks after last IP administration, or the subject's end of study, whichever is later.

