6.2 Demographics and Baseline Related Definitions

Age

Subject age at enrollment will be collected in years on the eCRF.

Baseline Lipid and Lipid-related Parameters

Baseline values for fasting lipids (total cholesterol, HDL-C, LDL-C, VLDL-C, non-HDL-C and triglycerides), ApoA1, ApoB100, ApoB48, hsCRP, Lp(a) and their derived parameters (e.g., ratio between them) are defined as the fasting concentrations

measured through central lab on Study Day 1. If for any reason a concentration for a parameter is not observed on Study Day 1, the closest prior to Study Day 1 measurement for the parameter to Study Day 1 will be used.

Body mass index (BMI)

Subject's BMI will be derived in kg/m² in the clinical database.

Other Baseline Values

For ECG data, the baseline value is defined as the nonmissing triplicate average of 3 (or all available) readings taken on Study Day 1. If the Study Day 1 reading is missing, the closest nonmissing triplicate reading prior to Study Day 1 will be used as the baseline.

For PCSK9, the baseline value is defined as the last non-missing value collected prior to or on Study Day 1, but must be prior to first IP administration.

For all other variables, the baseline value is defined as the last non-missing value collected prior to or on Study Day 1.

Change (Absolute Change) from Baseline

The arithmetic difference between a post-baseline value and baseline for a given time point:

Change (absolute change) from baseline = (post-baseline value – baseline value)

Percent Change from Baseline

The percent change from baseline for a given variable at a given time point is defined as:

[(value at a given time point – baseline value) / baseline value] x 100%

Baseline CHD Risk Factors

A subject will be categorized as having 2 or more CHD Risk Factors (Y/N) from the list of the modified NCEP ATP III risk factors:

- current cigarette smoking,
- hypertension,
- type II diabetes mellitus,
- family history of premature CHD as recorded on the eCRF, and
- low HDL-C defined as baseline HDL-C < 40 mg/dL in males and < 50 mg/dL in females.

Systematic Coronary Risk Estimation (SCORE) Categories

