10.6.2 Laboratory Test Results

Descriptive statistics will be provided for actual values and changes from baseline in select laboratory parameters at each protocol-specified scheduled visit. Laboratory analytes are provided in the protocol Table 2. Lab shift tables using the CTCAE v4.03 or later grading will be used for select analytes of interest, when applicable. The results will

be based on the maximum (i.e., worst) shift from baseline to the EOS. In addition, CK and liver function test (LFT) abnormalities will be assessed by the incidence overall and by visits of the following categories:

- CK > 5 x ULN
- CK > 10 x ULN
- ALT or AST > 3 x ULN
- ALT or AST > 5 x ULN
- Total Bilirubin > 2 x ULN
- (ALT or AST > 3 x ULN) and Total Bilirubin > 2 x ULN and Alkaline Phosphatase < 2 x ULN

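### No lipid-adjusted vitamin E is planned, so a lower plasma level on evolocumab could not be told apart from loss of the lipoproteins that carry it (exploratory; free improvement)

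*SAP*

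**What the plan says.** Protocol 7.7.6 lists the meal-test analytes: "plasma glucose, insulin, proinsulin, C-peptide, free fatty acids, glucagon, lipids, chylomicrons, ApoB48, IL-6, adiponectin, vitamin E". Vitamin E and lipids thus come from the same draws. On timing, SAP 3.1 states: "All subjects will complete a mixed meal tolerance test (MMTT) at the day 1 and week 12 study visits". Each test has a pre-meal fasting sample and one at 2 hours, with 1-hour and 3-hour samples added in the substudy. Vitamin E is among the results withheld from investigators along with the lipid panel: "IL-6, adiponectin, vitamin E, PK, and high sensitivity C-reactive protein (hsCRP) will be blinded until unblinding of the clinical database".

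The exploratory objective (Protocol 1.4, SAP 2.4) is comparative, evolocumab against placebo. The planned analysis in SAP 10.5.4 is one sentence: "Fasting and postprandial laboratory parameters of interest (including MMTT Extended Timepoints Substudy assessments) will be summarized at each scheduled assessment by treatment group". It does not name vitamin E, a metric or a statistic.

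Two other places might have supplied an adjusted value, and neither does:

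- SAP 6.2 provides for derived quantities in its lipid baseline definition ("derived parameters (e.g., ratio between them) are defined as the fasting concentrations"), but the list it applies to is fasting lipids, ApoA1, ApoB100, ApoB48, hsCRP and Lp(a).
- SAP 10.6.2, on laboratory results generally, offers only values and changes: "Descriptive statistics will be provided for actual values and changes from baseline in select laboratory parameters at each protocol-specified scheduled visit".

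On what the drug does to the carriers, Protocol 2.3.2 reports that treatment "was effective in lowering serum concentrations of LDL-C, total cholesterol, ApoB100, VLDL-C, triglycerides, Lp(a), non-HDL-C".

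**The concern.** Vitamin E is fat-soluble and circulates inside lipoproteins, LDL among them. This is general physiology that neither document states. If a drug removes part of the carrier, the concentration per volume of plasma falls even when each remaining unit of lipid holds as much vitamin E as before.

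A table of concentrations by arm would then show a lower value on evolocumab, and that number has two readings. One is that vitamin E went down with its carrier, as the drug's intended action would predict. The other is that the lipid left behind holds less vitamin E. A reader could take the first for the second. A true depletion could equally be dismissed as carrier loss. A lipid-adjusted value beside the raw one helps to tell them apart, and the lipids for it are already measured in the same samples.

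**Working it through.** **The plan's own figures.** The documents give no figure for vitamin E. The related figures are those for LDL-C in Protocol 10.2 and SAP 3.2, and they reproduce:

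- Attenuated effect: 0.85 × 35% = 29.75%, stated as 30%.
- Power: 300 and 150 less the 2% never dosed gives 294 and 147. With SD 30, SE = 30 × √(1/294 + 1/147) = 3.03, and 30/3.03 = 9.9. Two-sided power at 0.05 exceeds 0.9999, against a stated minimum of 99%.

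These figures are not in dispute. They supply the LDL-C falls used below.

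**Inputs**

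- LDL-C fall, L: 30% (planning effect), 50.33% (phase 2, 420 mg QM at week 12), 66.10% (phase 2, 140 mg Q2W at week 12).
- Share of plasma vitamin E carried in LDL, f: assumed 20-60%. This is not in the documents.
- Vitamin E per unit of lipid is held constant, so there is no depletion, and only the LDL-borne part changes.

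**Step 1. Expected change in the raw concentration:** −f × L.

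| LDL-C fall | f = 20% | f = 60% |
|---|---|---|
| 30% | 0.2 × 30 = 6.0% fall | 0.6 × 30 = 18.0% fall |
| 50.33% | 10.1% fall | 30.2% fall |
| 66.10% | 13.2% fall | 39.7% fall |

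Every entry arises with no depletion at all.

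**Step 2. Which denominator removes it.** Divide by a lipid measure of which a share g lies in LDL. On the same simplification, the ratio changes by (1 − f × L)/(1 − g × L) − 1. This is zero when g = f, that is, when the denominator represents the whole carrier. A broad measure such as total cholesterol, with or without triglycerides, approximates that. How closely it does so cannot be shown from the documents.

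**Step 3. LDL-C alone.** Here g = 1, so the ratio changes by (1 − f × L)/(1 − L) − 1:

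| LDL-C fall | f = 20% | f = 60% |
|---|---|---|
| 30% | 0.94/0.70 − 1 = +34% | 0.82/0.70 − 1 = +17% |
| 50.33% | 0.899/0.497 − 1 = +81% | 0.698/0.497 − 1 = +41% |
| 66.10% | 0.868/0.339 − 1 = +156% | 0.603/0.339 − 1 = +78% |

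With no change in vitamin E per unit of lipid, the ratio to LDL-C rises in every case. It would replace an expected fall with an artificial rise large enough to mask a real depletion.

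**The case against.** The strongest case against has four parts.

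**The premise is external.** The documents do not say that vitamin E travels in LDL, in what share, or that it falls in step with LDL-C. Protocol 2.3.2 also reports lower VLDL-C and triglycerides and higher HDL-C, so other carriers move and a fixed LDL share is a simplification. This stands. The percentages illustrate an assumption, and the fall is an expectation rather than a documented result.

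**The SAP does not say raw only.** SAP 10.5.4 leaves the metric open, so a summary of concentrations alone is inferred from the absence of any derived measure. This also stands. The criticism is that a useful quantity is not specified. It is not that a wrong one was chosen.

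**A reader might infer that the comparison between arms is confounded.** The documents do not support that. The arms are randomized, so the raw difference is a valid estimate of the effect on plasma vitamin E, which is what the exploratory objective asks about. Carrier loss would be a route by which that effect arises. Nor do the documents support an inference that evolocumab depletes vitamin E, or that the raw value should be dropped.

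**Little depends on it.** No test, threshold or statement on vitamin E status is planned, and lipids fall under the same summary sentence, so a reader could set the two group summaries side by side. This is correct as to stakes. It does not give a within-subject ratio, which is the quantity that addresses the question.

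**Conclusion.** The point holds as a free improvement. Vitamin E is measured with lipids in the same samples, a comparison between arms is the stated aim, and no lipid-adjusted value is planned. With an assumed 20-60% LDL share and constant vitamin E per unit of lipid, the plasma concentration would be lower by about 6-18%, 10-30% or 13-40% for LDL-C falls of 30%, 50% and 66%. That difference is a real effect on concentration. Taken alone, it does not say whether the cause is carrier loss or depletion.

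The conclusion rests on general physiology for the carriage of vitamin E and on an assumed share for the size. The endpoint is exploratory and descriptive, so no primary or secondary conclusion, significance level or sample size is touched.

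**What to change.** In SAP 10.5.4, before unblinding:

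1. Name vitamin E and keep the raw concentration in the table.
2. Beside it, report the ratio of vitamin E to total cholesterol, or to total cholesterol plus triglycerides. Choose one in advance and take both parts from the same pre-meal fasting sample, at day 1 and week 12.
3. For both quantities, give percent change from baseline and the evolocumab minus placebo difference within each dose frequency.
4. State that any comment on vitamin E depletion will rest on the lipid-adjusted value read together with the raw value.
5. Do not use LDL-C alone as the denominator.

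The cost is one derived variable and a few table rows, with no new sample, assay or visit. Fixing the denominator now also avoids choosing it after the results are known.
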